#### Pharmacotherapy for Obesity/Addiction (naltrexone-bupropion)

Recent studies have assessed the efficacy of combination treatments of long-acting acting opioid antagonists (naltrexone) and antidepressant drugs (bupropion) in lowering the body weight of obese patients. Bupropion seems to have a complementary effect of decreasing hunger in combination with naltrexone, producing significant long-term decreases in weight. A multicenter phase III trial was conducted that randomly assigned 1,742 overweight individuals to receive an oral preparation of a sustained release pharmaceutical. The intervention continued for 56 weeks after which mean reduction in body weight was significantly higher in the pharmaceutical groups than placebo groups. Pharmaceutical groups were treated with naltrexone 16 mg plus bupropion and 32 mg naltrexone plus bupropion. In the proposed study, dosing protocols will be followed for treatment of obesity: 1 tablet (90mg/8mg) initially week 1; increase by 1 tablet/day each subsequent week until daily maintenance dose of 2 tablets twice daily (360 mg bupropion/32 mg naltrexone) is achieved at the start of week 4. Use will be discontinued at month 4 if no clinical response is observed.

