The prevalence of FA is estimated to be 25% in the population of urban adult women who have a BMI classification of overweight or obese. Using this prevalence along with a medium effect size, a statistical power analysis was performed for sample size estimation with G\*Power 3.1. The design is a stratified four-group design with a pre and post measurement. Stratification by obesity phenotype (positive or negative for FA) will occur first, followed by random assignment to one of four treatment groups [Information Control (dietary and physical activity instruction), MI alone(diet and physical activity instruction supported by MI), MI((diet and physical activity instruction supported by MI+P(Contrave)). Using an  $f = 0.25$ , an  $\alpha = .05$  and  $\text{power} = 0.95$ , the a priori F test, analysis of variance, omnibus, one-way model gives a projected sample size of 252. As a pilot study, this study is underpowered for statistical hypothesis testing, and analyses will focus on descriptive statistics, estimation of effect sizes, and hypothesis generation and a sample of 40 eligible patients will be enrolled (10 in each group). This meets the pilot study guideline of at least 10% of a fully powered trial and remains realistic in terms of time and cost (Hertzog, 2008) while allowing for 50% attrition. It is expected that 25% of the population will meet the criteria of FA and therefore will need to screen and consent a total of 160 participants to reach the 40 people positive for FA. No more than 160 subjects will be consented for the entire pilot study.

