#### Data Collection

All research personnel will be CITI-trained. A nursing student will assist the nurse researchers with data collection. Each data collector will undergo fidelity checks (performed by the PI) for each measurement procedure before they will be allowed to collect data. They will also be trained in using the ASA24-2016® dietary recall, so they can assist the patients as needed.

The current version of the YFAS, the YFAS 2.0, will be used to assess participants obesity phenotype (positive or negative for FA). This measure adapts the eleven DSM-5 diagnostic criteria for substance-related and addictive disorders when the substance is HPFS foods. In order to meet the diagnostic threshold on the YFAS, individuals must report at least two of the eleven diagnostic indicators of FA plus clinically significant impairment or distress.

The Automated Self-Administered 24-hour Recall, version ASA24-2016® will be completed at each time point to assess changes in patients dietary intake. This web-based 24-hour dietary recall instrument has been used effectively by hundreds of researchers and has face validity and similar intake results to the AMP.10 A strength of the ASA24-2016® is that it includes most traditional American foods/ingredients.

Height: The patients height will be used in determining BMI and BIA measures. We will use the average of 2 heights (cm) measured with the Seca EC0123 stadiometer. During measurement, patients will be in socked feet with heels placed against the back of the platform and facing straight forward.

Body Composition: Bioelectrical impedance analysis (BIA) will be used to determine body composition. Estimated standard error for BIA is  $\pm$  3.5-5%. We will use a Tanita SC-250 body composition analyzer and follow a standardized protocol to measure percent body fat, body fat mass, fat free mass, percent body water, muscle mass, bone mass, BMI, and visceral fat. The software also classifies patients as underfat, healthy, overfat, or obese based on percent body fat, age and gender.

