If a subject experiences success in managing their weight while participating in the study,(which will be determined by a 5% decrease in BMI or body fat or total body mass over 4 months) the subject may continue with the weight management plan after completing all study related visits. All participants may continue with clinic visits following the study and may have available to them, usual care, MI, Contrave (unless they have taken it in the study and it was not effective), and bariatric surgery options. All subjects taking Contrave will be screened at each visit for suicidal ideation. In addition, they will be asked to call [name] immediately if they have any such feelings or symptoms of suicidal ideation. If they present with suicidal ideation, [name] will interview them using the Suicide Screening Algorithm (see documents) to determine the severity of the symptoms and make additional medical referrals as necessary. If the case is emergent, they will be immediately escorted to the ER or asked to come into the ER, if it is a phone visit. . If the case is urgent, they will be referred to psychiatric personnel in the office where [name] practices as a Psychiatric NP. They will be withdrawn from the study at this time and

[name] will be notified. [name] will follow up with these patients. At the six month visit a PHQ-9 and the YFAS (from the WALI) will be readministered. An appt for a 12 month sustainability measure will be set up.

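### Contrave takers with urgent suicidal ideation leave the study, not only the drug, so drug versus non-drug effect sizes are open to a very small arm-specific loss of outcomes

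*Combined protocol and SAP*

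**What the plan says.** The suicidal-ideation paragraph near the end of Data Collection sets the rule. "All subjects taking Contrave will be screened at each visit for suicidal ideation". A person who presents with ideation is interviewed "using the Suicide Screening Algorithm (see documents) to determine the severity of the symptoms". Emergent cases go to the emergency room and urgent cases to psychiatric personnel. The next sentence reads "They will be withdrawn from the study at this time", and a named role "will follow up with these patients". The same paragraph then gives a PHQ-9 and a repeat YFAS at the six-month visit, and an appointment for a 12-month measure, without saying whom these cover.

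The rule for lack of response is worded differently: "Use will be discontinued at month 4 if no clinical response is observed" (Pharmacotherapy section, repeated under Intervention Conditions). It stops the drug and does not mention leaving the study.

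For the other arms, suicidal ideation appears only in the list of initial eligibility screens. The sample-size paragraph under Contribution to Science says that "analyses will focus on descriptive statistics, estimation of effect sizes, and hypothesis generation".

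**The concern.** Stopping a drug and ending follow-up are separate decisions. Here a safety event after randomisation ends both, and the rule is written for two of the four arms. Someone withdrawn for ideation at month 2, say, would have no described BMI, body composition, waist, blood pressure or dietary recall at month 6. The estimate for that drug arm would then rest on those who did not have the event.

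The comparisons exposed are drug against non-drug, such as P versus IC and MI+P versus MI. MI versus IC is untouched. In MI+P versus P the same rule applies to both arms. Because the pilot is meant to estimate effect sizes, an avoidable loss tied to assigned arm is worth removing if that costs little.

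**Working it through.** **Reading the text.** The withdrawal sentence directly follows the urgent cases. Covering emergent cases as well is the natural reading but is not spelled out. The follow-up sentence comes straight after the psychiatric referral and names no study measure, so it reads as clinical care. The six-month PHQ-9 and YFAS, even if they did reach withdrawn participants, would not supply biometric or dietary outcomes. Data gathered before withdrawal remain; the ASA24, for example, "will be completed at each time point to assess changes in patients dietary intake".

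**Inputs from the plan.**
- Enrolment of 40, ten per group (Contribution to Science): two drug arms × 10 = 20 on drug.
- Alternatively, ten per phenotype-by-treatment cell (Initial Screening for Eligibility): 2 phenotypes × 2 drug arms × 10 = 40 on drug.
- Six months of intervention; 50% attrition allowed for.

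**Inputs assumed.** The documents give no ideation or withdrawal rate, so there is no figure of the plan's own to reproduce on this point. I take r = 1% to 5% for urgent or emergent ideation over six months, and d = 0.5 to 1 SD for the outcome difference between a person who leaves and the rest of the arm.

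**Expected exits,** n × r, and **chance of at least one,** 1 − (1 − r)^n:

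| On drug | r | Expected exits | Chance of at least one |
|---|---|---|---|
| 20 | 1% | 0.2 | 18% |
| 20 | 2% | 0.4 | 33% |
| 20 | 5% | 1.0 | 64% |
| 40 | 1% | 0.4 | 33% |
| 40 | 2% | 0.8 | 55% |
| 40 | 5% | 2.0 | 87% |

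**Shift if one person leaves an arm of n.** The full-arm mean differs from the mean of those remaining by d/n. The standard error of a difference between two arms of n, in SD units, is √(2/n).
- n = 10 (one exit is 10% of the arm): shift 0.5/10 = 0.05 to 1/10 = 0.10 SD; SE √(2/10) = 0.447; ratio 0.11 to 0.22.
- n = 20 (phenotypes pooled; one exit is 5%): shift 0.5/20 = 0.025 to 1/20 = 0.05 SD; SE √(2/20) = 0.316; ratio 0.08 to 0.16.

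**Expected shift, allowing for the chance that nobody leaves,** r × d: 0.01 × 0.5 = 0.005 SD to 0.05 × 1 = 0.05 SD. Against 0.447 that is 0.01 to 0.11 of a standard error; against 0.316 it is 0.02 to 0.16.

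These standard errors assume that everyone else is retained. With the 50% attrition allowed for, an arm of ten becomes five and the standard error rises to √(2/5) = 0.632.

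**The case against.** The strongest reply is that this does not matter. The plan calls itself underpowered for hypothesis testing and allows for half the sample to be lost. With 20 on drug, the chance that nobody leaves under this rule is 36% to 82% on the assumed rates. Entrants are already screened for ideation, and non-responders stop the drug at month 4, so six months of exposure is a generous window. All of this stands, and it is why the point is minor.

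Second, ending research participation for someone sent to the emergency room or to psychiatric care is a defensible protective choice. That also stands. The change proposed alters neither the screening nor the referral, and it makes later measurement depend on the participant's agreement and clinical judgement.

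Third, the Statistical Methods section says missing data will be evaluated and EM or multiple imputation considered. Together with the data collected before withdrawal this helps somewhat, but it is not a commitment and says nothing specific to these withdrawals. The 50% allowance covers how many are lost, not whether the loss differs by arm.

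Fourth, the asymmetry rests partly on silence. A reader might infer that IC or MI participants with ideation would be kept in follow-up; the documents do not say what happens to them. What can be said is that the mandatory rule is written only for Contrave takers. A reader might also infer that any ideation, however mild, leads to withdrawal. The text reaches urgent and, on the natural reading, emergent cases; grading rests on an algorithm that is not among the documents reviewed, so nothing is claimed about milder cases.

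**Conclusion.** The point holds as a cheap improvement of minor severity. As written, the plan ends study participation for a safety event in MI+P and P only, and provides for no biometric or dietary outcomes afterwards. About 0 to 2 participants would be affected under assumed rates of 1-5%. One exit would move an arm mean by 0.08 to 0.22 of a standard error under assumed differences of 0.5 to 1 SD, and the expected effect is smaller still. The direction is unknown, because the documents do not indicate how those who leave would differ.

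A reader might infer that the drug effect sizes will be materially biased. The documents do not support that: the rate and the difference are both assumptions, earlier data remain, and the shift lies well within sampling error. It would not change a conclusion. Nor is the decision to stop the drug in question.

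**What to change.** In the suicidal-ideation paragraph of Data Collection, replace the withdrawal wording with:

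> Contrave is stopped and the participant is referred as above; with the participant's agreement and where clinically appropriate, the scheduled biometric and ASA24 measures and the six-month questionnaires are still collected, and the participant is analysed in the assigned arm.

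Screening and referral stay as written. Stopping the drug stays mandatory, as withdrawal from the study now implies.

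The cost is one sentence and visits already on the schedule. Three limits should be accepted openly. A few participants in psychiatric care would be asked to attend outcome visits, and some will decline, so recovery is partial. Confidence and importance scores are recorded during MI sessions, so they are not recovered once those sessions end. Analysis in the assigned arm is an analysis rule that the plan states nowhere else, and it should be carried into the Statistical Methods section.

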#### Statistical Methods to Analyze Data

Missing data will be evaluated. For summated scales on which fewer than 20% of an individuals responses are missing, the individuals mean on the remaining items may be substituted, as appropriate. For analyses requiring complete data, imputation of missing values using the EM algorithm or multiple imputations will be considered, as appropriate. Scoring algorithms for each instrument will be used per the published use manual. Each statistical test will be conducted at  $p=.05$  level. Data will be analyzed using descriptives (means, medians, standard deviations of scores), independent t-tests, correlation coefficients and analysis of variance. In Aim 1, ANOVA will be used to assess differences between the three treatment groups on the YFAS to determined changes in MI confidence, importance and readiness to change scores as well as ASA24-2016® dietary recall and biometric measures. Correlational analysis will be used to explore the relationships between ASA24-2016® dietary recall and biometric measures. In Aim 2 independent t-test will be used to determine if the positive and negative YFAS groups differ across treatment responses.

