#### Proposed methods/approach

Investigators propose assessing obese clients with the YFAS as part of their intake once they are referred to the Healthy Behaviors Clinic by Regional West physicians/practitioners. A nurse researcher with expertise in MI and a nurse practitioner will perform intake assessments, obtain consent and randomly assign participants in each phenotype (positive or negative for FA) to one of three treatment groups (usual care, individual MI alone, and individual MI with pharmacotherapy). Interventions will occur over 6 months. A clinical psychologist with expertise in the YFAS (University of Michigan) will serve as a consultant on this project and a registered dietitian (University of Nebraska Lincoln) will serve as a co-investigator.

Investigators expect that MI and MI+P and P will be more effective in improving outcome measures than IC. We also expect that response to the treatments will differ between the two obesity phenotypes (those testing positive and those testing negative for FA).

To determine if MI alone or MI+P or P is effective in treating obese patients with and without FA (based on the YFAS) as determined by :

- Higher MI confidence, importance and readiness to change scores
- Reduced intake of foods that are highly processed and high in fat and sugar (HPFS) and increased intake of complex carbohydrate foods(fresh fruits, vegetables, whole grains) and minimally processed proteins (nuts, fresh meats) (ASA24-2016® dietary recall)
- Improved biometric measures (BMI, body composition, waist circumference, and blood pressure)

-To determine whether the two obesity phenotypes (with and without FA) differ in their response to the four treatments.

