**Initial Screening for Eligibility (Suicidal Ideation, Pregnancy test (urine test), Lactation, Recruitment):**  
Participants will be recruited from obese patients referred to the Healthy Behaviors Clinic by Regional West Physicians. Nurse researchers who work at the Healthy Behaviors Clinic will inform potential participants about the study and, if they agree to participate, will consent them.

Both treatment groups, Those who test positive for and those who test negative for FA (food addiction) will be assigned to one of four treatment arms, IC, MI, MI+P and P. All will receive dietary and exercise information. After consenting, each participant will be administered the YFAS to determine their obesity phenotype (positive or negative for FA). Participants within each phenotype will be randomly assigned to one of the intervention (MI or MI+P, or P) or the IC information control (diet and physical activity instruction, which will be no less than current standard of care) treatment groups using a randomization schedule (assignments in numbered, sealed, opaque envelopes; one set for each phenotype) 1:1:1:1 ratio, provided by our statistician, [name]. Phenotype assessment and treatment assignment will continue until the sample size (n=10) is met for each phenotype-treatment group category. Those in the control group will be seen at the same time periods as each treatment group to maintain their interaction time with the clinic. They will receive diet and exercise instruction at each time point.

**Intervention Conditions (MI, MI+P):** MI is theorized to decrease a patient's ambivalence and increase his/her perceived behavioral control (self-efficacy) for limiting HPFS and increasing CC intake by emphasizing personal choice and control in decision-making and by affirming the patient's self-management ability. Interventionist nurses will deliver MI sessions following data collection at baseline, 1, 2, 3, and 4 weeks and 2, 3, 4, 5, and 6 months to promote sustained behavioral change. A written MI algorithm will be used to ensure uniform implementation of the intervention.

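### The pilot is said to be for estimation, but the analysis section specifies only descriptives and tests at .05, with no difference from IC, treatment effect size or confidence interval

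*Combined protocol and SAP*

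**What the plan says.** Three places in the combined protocol and SAP bear on this.

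- **Contribution to Science (sample-size text).** The pilot's purpose is stated plainly: "this study is underpowered for statistical hypothesis testing, and analyses will focus on descriptive statistics, estimation of effect sizes, and hypothesis generation". The fully powered calculation appears beside it: "omnibus, one-way model gives a projected sample size of 252", at f = 0.25, alpha .05 and power 0.95. The pilot itself is smaller: "a sample of 40 eligible patients will be enrolled (10 in each group"), allowing for 50% attrition.
- **Proposed methods/approach.** The first aim is confirmatory: "To determine if MI alone or MI+P or P is effective in treating obese patients with and without FA". It is judged on MI scores, dietary intake and biometric measures. The stated expectation is that MI, MI+P and P each do better than IC.
- **Statistical Methods to Analyze Data.** This is the only analysis section. After means, medians and SDs it lists t-tests, correlation coefficients and ANOVA: "Each statistical test will be conducted at" the .05 level. For Aim 1, "ANOVA will be used to assess differences between the three treatment groups on the YFAS"; for Aim 2, a t-test compares the two phenotypes. It names no contrast with IC, treatment effect size, confidence interval, primary outcome or analysis visit.

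**The concern.** An analyst who follows the analysis section to the letter does not produce what the sample-size text promises. An omnibus ANOVA p-value says whether the arms differ somewhere. It does not give the MI, MI+P or P difference from IC, which is the question the aims pose, and it gives no estimate with a stated precision to carry to a larger trial.

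Fixed-level tests combined with an aim of deciding whether treatments are effective also invite readers to take p < .05 as the result. At this sample size that filter passes mainly large chance deviations, and it is applied to several outcomes. The pilot's most useful products would be estimates, their uncertainty and the SDs. Of these, the section specifies only the SDs.

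**Working it through.** **1. The plan's own figure.** One-way omnibus F test, noncentrality λ = N·f², df = k − 1 and N − k, f² = 0.0625.

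- k = 3, N = 252: λ = 15.75, power 0.951. This reproduces the plan's 252.
- k = 4: the smallest equal-group N that reaches 0.95 is 280; at N = 252 power is 0.926.

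So 252 corresponds to three groups, although "The design is a stratified four-group design with a pre and post measurement". That is a separate matter. The formula is confirmed and is used below with four arms.

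**2. Power of the planned ANOVA in the pilot (k = 4, f = 0.25, alpha .05).** Three values of N cover the text: 40 as stated; 20 after the allowed 50% attrition (40 × 0.5); and 80 if recruitment runs "until the sample size (n=10) is met for each phenotype-treatment group category" (8 cells × 10). The last three columns are simulated under a true f of 0.25.

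| N | λ | Power | Mean observed f if p < .05 | Ratio to 0.25 | Ratio, bias-adjusted f |
|---|---|---|---|---|---|
| 40 | 2.5 | 21% | 0.59 | 2.4 | 1.9 |
| 20 | 1.25 | 12% | 0.94 | 3.8 | 3.0 |
| 80 | 5.0 | 42% | 0.41 | 1.6 | 1.4 |

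At N = 40 the critical F(3, 36) is 2.87, so the observed f must exceed √(2.87 × 3/36) = 0.49 to reach significance, about twice the assumed effect. Part of the ratio is the upward bias of a sample f, which cannot be negative: over all simulated trials at N = 40 its mean is 0.37. The last column removes most of that bias, and the exaggeration remains.

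**3. One arm against IC.** The plan gives no pairwise effect. As an assumption take d = 0.5, the two-group equivalent of f = 0.25 (d = 2f). A two-sample t-test has 19% power at 10 per arm, and significant estimates average 2.2 times the truth. At 5 per arm the figures are 11% and 2.9; at 20 per arm, 34% and 1.7.

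**4. What estimation would deliver.** The 95% CI half-width in SD units is t(.975, 2n − 2) × √(2/n):

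- n = 10: 2.101 × 0.447 = 0.94 SD
- n = 5: 2.306 × 0.632 = 1.46 SD
- n = 20: 2.024 × 0.316 = 0.64 SD

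**5. Number of outcomes.** The documents give no count. By named domain under Proposed methods/approach there are 3 MI scores, 2 or 3 dietary measures and 4 biometric measures, so 9 or 10. Splitting blood pressure into systolic and diastolic, and body composition into the seven analyser variables other than BMI listed under Data Collection, gives 3 + 3 + 1 (BMI) + 7 + 1 (waist) + 2 = 17.

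**6. Chance of at least one false positive in one set of tests, all nulls true.** If independent, 1 − 0.95^m:

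- m = 9: 37%
- m = 10: 40%
- m = 14 (17 without the three MI scores): 51%
- m = 17: 58%

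For 17 outcomes with an assumed common correlation, simulated for four arms of 10, the chance is about 51% at 0.3, 41% at 0.5, 28% at 0.7 and 17% at 0.9. A two-arm simulation gave 49%, 39% and 27% at 0.3, 0.5 and 0.7. Simulation error is of the order of one percentage point. Aim 2 tests, correlations and repeated visits are not counted.

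**7. Would a multiplicity correction help?** Bonferroni over 17 tests gives .05/17 = .0029. The N = 40 ANOVA then has 3% power, so the correction would remove almost all power and still give no estimate.

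**The case against.** The strongest reply is that the document already calls itself exploratory. It commits to effect sizes in the sample-size text, and the analysis section opens with descriptives from which standardised differences can be computed. Correlation coefficients are effect measures too, and a nominal .05 level can coexist with an exploratory purpose. On this view the fault is incomplete specification, not contradiction.

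Much of that stands, and it rules out several stronger readings that a reader might infer:

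- *That the plan has no effect sizes.* The sample-size text makes them a focus. What is missing is their specification in the section that the analyst will follow.
- *That 17 outcomes will be tested.* The documents do not say so. Seventeen requires splitting the output of one analyser into overlapping variables. Data Collection also has the MI scores recorded during MI sessions, so they may not exist in the IC and P arms.
- *That a false positive is likely.* Only the independent cases with 14 or more outcomes clearly exceed one half, and independence is implausible for body-composition measures.
- *That outcomes will be chosen by p < .05 and a later trial sized on them.* No such rule is written. The exaggeration figures show what would follow if significance were used that way.

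What the reply does not meet is that the aim is worded as deciding effectiveness, that the listed tests do not estimate any arm's difference from IC, and that no interval is planned anywhere. Correlations between diet and biometrics are not treatment effects.

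**Conclusion.** The concern holds as a mismatch within the document: the purpose is estimation, but the only analysis section specifies descriptives and fixed-level tests. It does not depend on the number of outcomes.

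Under the plan's own f = 0.25 with four arms, the planned ANOVA would reach significance in 12% to 42% of trials across N = 20 to 80. The observed f in those trials would be about 1.6 to 3.8 times the truth (1.4 to 3.0 after bias adjustment). The chance of at least one false positive per set of tests is substantial but uncertain: 37% to 58% for 9 to 17 independent outcomes, and about 27% to 51% for 17 outcomes at assumed correlations of 0.7 to 0.3. The correlations, the outcome count and the pairwise d = 0.5 are assumptions. The effect size f, alpha and the sample sizes come from the document.

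A reader might conclude that a multiplicity adjustment is required. The figures do not support that; the remedy is to report estimates with intervals. Nor do the documents support naming BMI, or any other measure, as the lead outcome on the sponsor's behalf: Data Collection itself presents waist circumference as the better indicator of body fat.

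**What to change.** In Statistical Methods to Analyze Data, replace the .05 sentence and the Aim 1 and Aim 2 test sentences with:

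> For each outcome measured in all arms, the main result is the difference of each of MI, MI+P and P from IC in change from baseline to month 6, with its 95% CI and standardised effect size, overall and by phenotype. The difference between phenotypes in each treatment effect is reported in the same way. P-values are unadjusted and exploratory and are not used to call a treatment effective.

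In Proposed methods/approach, reword the first aim ("To determine if MI alone or MI+P or P is effective in treating obese patients with and without FA") to begin *To estimate the effect of*. If a lead outcome is wanted, the sponsor chooses it before the data are analysed. The descriptive summaries and the exploratory correlations can stay, and scores recorded only in the MI arms can be summarised descriptively there.

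Cost: wording in two sections, with no extra data or visits. The intervals will be wide (about ±0.94 SD at 10 per arm), and by-phenotype estimates depend on which sample size applies, so the two statements of 40 in total and 10 per phenotype-treatment cell should be reconciled at the same time. The trial gives up claims of significance that its own sample-size text says it cannot support.
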